6.5 Safety Analysis

The safety analyses described in this section will be conducted on the safety population. No formal statistical testing is planned for the safety parameters.

6.5.1 Treatment Exposure

Duration of exposure will be defined as number of days on treatment (computed as date of last dose – date of first dose + 1) for each subject. Date of last dose of study drug will be derived as the latest date of variable EXENDAT and date of first dose of study drug will be derived as the earliest date of variable EXSTDAT both on Investigational Product Use Form. In subjects with a comment indicating unknown date of first dose, randomization date will be used. In addition, if the date of last dose is missing the minimum of Week 12 visit date or study completion date will be used. Duration of exposure will be summarized overall and by treatment group. Duration of exposure will also be categorized according to 14 days intervals ([1-14], [15-28], [29-42], etc.) and summarized accordingly using frequencies and percentages, overall and by treatment group. Summary of study treatment discontinuation will also be presented overall and by treatment group.

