5.5 Interruption or Discontinuation of Investigational Product

Study participants may be interrupted or discontinued from the IP if any of the following occur:

1. A IP-related adverse event or other reason which, in the investigator's opinion, will jeopardize the subject's participation in the study or the interpretation of study data (e.g., severe intercurrent illness requiring additional care measures or preventing further dosing)
2. Significant tolerability issues
3. Participant's decision

At the time of IP interruption, the study site will document in the eCRF the reason for IP discontinuation. The study participant should continue to be followed for all other study related procedures and visits, and clinical study outcomes and evaluation.

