3.3 Safety Population

The safety population will include all randomized subjects who received at least one dose of IP (i.e. subjects with at least one non missing Investigational Product treatment period start date (variable EXSTDAT or a comment indicating unknown date of first dose) on Investigational Product Use Form of the eCRF). Subjects will be assigned to treatment groups as per actual treatment received for analysis purposes.

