6.3.6 Treatment Compliance

An overall compliance calculation will be performed using primarily the study administration intake recorded on the Drug Accountability Form of the eCRF or on the Investigational Product Use Form of the eCRF if information regarding study medication returned/lost is missing. Compliance for the whole study is derived as follows:

| | | |
|------------------------|-----------------------|---|
| | Pill counts (%) | $\frac{[\text{sum of caplets dispensed} - \text{sum of caplets returned} - \text{sum of caplets lost}] \times 100}{[\# \text{ caplets to take per day} \times (\text{date last scheduled visit} - \text{date rando})]}$ |
| Compliance overall (%) | Days on treatment (%) | 
If # of caplets dispensed ≠ missing AND If information regarding study medication returned is missing (i.e. # of caplets returned is missing and/or # of caplets lost is missing)
 $\frac{[\text{date of last dose} - \text{date of first dose}] \times 100}{[\text{date last scheduled visit} - \text{date rando}]}$ |
| | NA | 
If # of caplets dispensed = missing OR If last scheduled visit = baseline
 |

Where

- Cohort 1 (rando number 001 à 280): Number of tablets dispensed = 147 (# caplets per day = 3)
- Cohort 2 (rando number 281 à 563): Number of tablets dispensed = 294 (# caplets per day = 6)
- Cohort 3 (rando number 564 à 997): Number of tablets dispensed = 588 (# caplets per day = 12)

Compliance will also be categorized as follow: < 80%, [80%-120%] or >120% and summarized accordingly using frequencies and percentages, by treatment arm, for the subjects of the ITT population.

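### Exposure and the fallback compliance measure use only the first and last dose dates, so an interruption followed by resumed dosing is counted as time on treatment

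*SAP*

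**What the plan says.** **Exposure.** SAP 6.5.1 says: "Duration of exposure will be defined as number of days on treatment", and this number is "computed as date of last dose – date of first dose + 1". On the inputs it says: "Date of last dose of study drug will be derived as the latest date of variable EXENDAT". The first dose is the earliest EXSTDAT. Only these two outer dates enter. The rule for a missing end date is: "if the date of last dose is missing the minimum of Week 12 visit date or study completion date will be used".

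**Compliance.** SAP 6.3.6 derives overall compliance "using primarily the study administration intake recorded on the Drug Accountability Form of the eCRF", that is, from a pill count. A fallback labelled *Days on treatment (%)* divides (last dose − first dose) by (last scheduled visit − randomization). It applies when the dispensed count is known and this condition is met: "If information regarding study medication returned is missing (i.e. # of caplets returned is missing and/or # of caplets lost is missing".

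**Per-protocol sets.** SAP 3.2 requires at least 80% compliance and names the Drug Accountability Form as the source. SAP 6.4.4.1 repeats the analysis at 70%.

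**Interruptions.** Protocol 5.5 says: "Study participants may be interrupted or discontinued from the IP if any of the following occur". Protocol 4.3 and 7.3 also speak of temporary discontinuation. Protocol 5.3 has product that was not taken, or only partly taken, reported in the eCRF with the reason. SAP 3.3 identifies treated subjects by "at least one non missing Investigational Product treatment period start date", so the form can hold more than one treatment period.

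**The concern.** The label and the formula disagree. A span from first to last dose equals days on treatment only when dosing was continuous. If a subject stops for some weeks and then resumes, the weeks off product lie inside the span and are counted as treatment.

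Two outputs are at stake:

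- **The exposure summary (Table 3.1.1)**, including its 14-day bands. No planned table or listing shows interruption days. Table 3.1.2 covers discontinuation, and the eight listings include none for dosing or compliance.
- **The per-protocol analyses**, conditionally. SAP 6.4.4.1 adds the 70% set to show the impact of compliance. It would do that poorly if subjects with long gaps were scored at 100%.

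The missing-date rule is a related but separate matter. Protocol 4.3 and 5.5 ask subjects who stop product to stay in follow-up, so the Week 12 visit can fall long after the last tablet.

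**Working it through.** The plan states no figure to reproduce, so I applied its formulas to constructed cases.

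**Inputs.** Randomization and first dose on day 1; last dose and last scheduled visit on day 84 (the scheduled Week 12 day in SAP Appendix 2); thresholds of 80% and 70%.

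**Worked case: product taken on days 1–28 and 78–84.**
- Days on product: 28 + 7 = 35, which is 35/84 = 41.7% of the period.
- SAP exposure: 84 − 1 + 1 = 84 days, band 71–84. The true figure falls in band 29–42.
- SAP fallback compliance: (84 − 1)/(84 − 1) = 100%, above both thresholds.
- SAP pill count: 35/83 = 42.2%, below both thresholds.

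**Gaps of g days, then resumed dosing up to day 84.** Net exposure = 84 − g. Pill count = (83 − g)/83, which sets an uninterrupted subject at 100%.

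| Gap (days) | SAP exposure | Net exposure | SAP fallback | Pill count | Sets met by pill count |
|---|---|---|---|---|---|
| 0 | 84 | 84 | 100% | 100% | both |
| 14 | 84 | 70 | 100% | 83.1% | both |
| 21 | 84 | 63 | 100% | 74.7% | 70% only |
| 28 | 84 | 56 | 100% | 66.3% | neither |
| 56 | 84 | 28 | 100% | 32.5% | neither |

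The two SAP first-to-last measures do not move with g. A gap-deducted fallback would follow the pill-count column. Status changes at 17 days for the 80% set (66/83 = 79.5%) and at 25 days for the 70% set (58/83 = 69.9%). Counting the last day as a full dosing day moves each limit by one day. With the visit on day 79 or day 89, the ends of the scheduled window, a 28-day gap gives 50/78 = 64.1% or 60/88 = 68.2%, so it fails both thresholds across the window.

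**Permanent stop with a recorded date.** Last dose on day 28, visit on day 84: exposure is 28 days and the fallback is 27/83 = 32.5%. Both are sensible.

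**Permanent stop, last-dose date missing.** Product stopped on day 14, visit and completion on or after day 84: the imputed exposure is at least the 84 days to a day-84 visit, against a true 14. SAP 6.3.6 states no matching imputation for the fallback.

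**The case against.** A reader might infer that any subject interrupted for weeks can enter both per-protocol sets. The documents do not support that.

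- The default compliance measure is the pill count, and it excludes the worked case from both sets.
- Exposure plays no part in per-protocol membership.
- SAP 3.2 names only the Drug Accountability Form, whereas the fallback uses dates from the Investigational Product Use Form. Nothing says that fallback values feed the criterion.
- The sponsor may also class other deviations as major.

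A reader might also infer that both measures fail for everyone who stopped. They do not: a permanent stop with a recorded last-dose date is handled correctly.

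Nor can the fallback be called common. Its trigger is broad, since a blank lost count is enough even when the returned count is known. But no rate of missing counts is given, and protocol 5.3 asks for all unused tablets and containers back at each visit. Any distortion between dose tiers is likewise conditional on interruption rates that the documents do not state. The discontinuation summary, the adverse events leading to withdrawal and the compliance categories by arm give partial cover.

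Finally, several EXSTDAT and EXENDAT records do not prove that periods are split at interruptions. Kits are dispensed at Week 0 and Week 6, so the records may simply be one per kit.

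All of this stands, and it narrows the point. It does not remove the mismatch between label and formula. It also leaves SAP 3.2 open: if the fallback feeds the criterion, long gaps can pass; if it does not, the SAP has no stated per-protocol rule for subjects with missing counts.

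**Conclusion.** The point holds in limited form. For a subject who interrupts and resumes, the stated rules give a wrong exposure figure and, where the fallback is used, a wrong compliance figure: 84 days and 100% against 35 days and about 42% in the worked case. Entry to the per-protocol sets is affected only if a returned or lost count is missing and the fallback feeds the criterion. The missing-date rule can over-credit an early stopper who remains in follow-up.

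The ITT primary analysis is unaffected. What is exposed is a descriptive safety table and, conditionally, a sensitivity analysis. The size in the trial cannot be stated, because rates of interruption, missing counts and missing last-dose dates are not given. The figures assume first dose on the day of randomization and full dosing outside the gap.

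**What to change.** 1. **SAP 6.5.1:** compute days on treatment as the distinct calendar days covered by the recorded treatment periods, so that a date shared by two periods counts once. If periods are not split at interruptions, use the first-to-last span minus the interruption days recorded in the eCRF. Add to Table 3.1.1 the number of subjects interrupted and the days interrupted, by arm.
2. **SAP 6.3.6:** use the same gap-deducted days as the fallback numerator. Count end days alike in numerator and denominator; otherwise an uninterrupted subject scores 84/83 = 101.2%.
3. **SAP 3.2:** state whether the fallback feeds the 80% and 70% criteria and, if not, how subjects with missing counts are classified.
4. **Missing last-dose date:** use the last date with intake documented in the eCRF. Attendance at a visit is not itself evidence of intake. Use the Week 12 or completion date only if nothing shows an earlier stop.

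The cost is SAP wording and minor programming, after a check of how the annotated CRF records interruptions. The intake card goes back to the site, but the documents do not say that it is entered in the eCRF, so it may not be usable. A few subjects may leave the per-protocol sets, and the exposure figures become slightly less favourable.

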6.5.2 Adverse Events and Serious Adverse Events

6.5.2.1 Adverse Events

AEs will be coded by system organ class and body system according to the MedDRA dictionary (version 22.0).

The total number of TEAEs reported, the number and proportion of subjects experiencing at least one TEAE, at least one severe TEAE, at least one TEAE related to the study treatment, and at least one TEAE leading to drug withdrawal will be presented. In addition, number and proportion of subjects experiencing a treatment-emergent AE will be presented by system organ class and preferred term overall and for each treatment group.

A treatment-emergent AE will be defined as an AE with onset date on or after the date of first dose. If it is not possible to assess the timing of the start of the AE to the date of first dose due to incomplete AE onset date and/or incomplete date of first dose, the event will be assumed to be treatment-emergent.

All AEs will be listed but only treatment-emergent AEs will be summarized.

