6.2 Randomization and Treatment Procedures

Urine pregnancy test is repeated in females of childbearing potential at the randomization Visit 2.

Subjects considered by the investigator to meet all entry criteria are scheduled for randomization at Week 0 (Visit 2) where subject receives either CP105F (1.5 g, 3 g or 6 g) or matching placebo in a double-blinded fashion. Dietary counselling per Appendix 1, and IP and statin (for subjects who are taking statins) administration instructions are reviewed with the subject at each dispensing visit (Visits 2 and 3), and IP and statin (for subjects who are taking statins) compliance is assessed at subsequent visits (Visits 3 and 4):

- IP administration: 1, 2 or 4 tablets (based on the dosing arm currently recruiting) taken TID in the morning before breakfast, at mid-day before lunch and before supper time preferably at the same times every day. Subjects should be clearly instructed that if a dose is missed, the next regularly scheduled dose should be taken and unused tablets returned at the next study visit.
- Statin administration (for subjects who are taking statins): in the evening or least 2 hours after the last dose of IP.

During the 12-week treatment period, visits will take place at Weeks 6 and 12 (Visit 3 and 4 respectively, \pm 5 days), followed by a Safety Follow up (Visit 5, \pm 5 days) at Week 14.

Subjects will continue to receive dietary counselling throughout the course of the treatment period and have labs measured as outlined in Appendices 2 and 3. Subjects will be assessed for compliance to IP through pill counts (see section 5.3). At each visit, subjects will be questioned in a non-specific manner for the occurrence of Adverse Events.

Safety assessments may be done at any time during the subject's participation in the study. Follow-up phone call will be performed 2 weeks after last dose taken for capturing any AEs.

6.3 Medical History:

Medical History will consist of detailed information, with particular attention to identify factors that would exclude a patient, including: age, race, sex, current medications, drug sensitivities or any adverse reactions to medications, history of hepatic, renal, or cardiovascular disease,

smoking history, alcohol intake, drug abuse, prior hospitalizations, surgeries, interventions, and serious illnesses

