6.9 Adverse Events

Adverse events (serious and non-serious) will be collected throughout the study from randomization to last dose of IP taken. SAEs will be collected from the time of consent through to 2 weeks after the last dose of study product. At each visit, the investigator or designated qualified study site staff will ask the subject if any untoward medical event occurred since the last visit. For each event, the date of onset and end, severity, relationship to IP, outcome and treatments administered for the event will be recorded in the eCRF.

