7.4 Time Period, Frequency, and Method of Detecting AEs and SAEs

All serious adverse events (SAEs) will be captured from the time of consent through to week 14 safety Follow up phone call. All AEs will be captured between the time of randomization up to the last dose IP taken. Each study participant will be monitored by the investigator and study staff for AEs/SAEs occurring throughout the study. The investigator or designee will enquire about AEs/SAEs in a non-specific manner through the study at all visits.

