During the treatment period, subjects will return to the study site at Visit 3 (Week 6) and at the End of Treatment Visit (Week 12) for laboratory tests and clinical assessments, including for Adverse Events (AEs), dietary guidance and IP compliance. At the Safety Follow-up Visit (Week 14), subjects will be contacted via telephone for an assessment of Adverse Events (AEs). Time window for the Visit 3 (Week 6), Final Visit (Week 12) and Safety Follow-up Visit is ± 5 days.

[figure not shown]
Laboratory tests and clinical assessments will be performed as noted in the schedule of visits (Appendix 1).

Safety and tolerability assessment will include AEs, hematology, biochemistry, physical examination, vital signs and electrocardiogram (ECG).

The study design is presented in the following figure.

* Subjects treated or not with a statin at baseline

W-1 (up to -7 day)

W0

W6 (\pm 5 days)

W12 (\pm 5 days)

W14 (\pm 5 days)

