5.2 Serious Adverse Events

A serious adverse event is a noxious and unintended response to a natural health product that occurs at any dose and that requires in-patient hospitalization or prolongation of existing hospitalization that causes congenital malformation, results in persistent or significant disability or incapacity, is life-threatening or results in death.

SAEs will be collected from the time of consent through to 2 weeks after the last dose of study product.

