9 APPENDICES

9.1 Appendix 1 - Schedule of visits

| Procedure/Visit | Screening Period (V1) | Randomization Baseline Visit (V2) | Visit 3 (V3) | End of Treatment Visit (V4) | Safety Follow-up Visit (V5) (telephone) |
|---|--------------------------|---|----------------------|-----------------------------------|--|
| | Week -1 Up to 7 days | Week 0 | Week 6 (± 5 days) | Week 12 (± 5 days) | Week 14 (± 5 days) |
| Informed consent form | X | | | | |
| Inclusion & Exclusion criteria | X | X | | | |
| Medical History | X | X | | | |
| Demographics | X | | | | |
| Physical examination | X | | | X | |
| Vital signs (blood pressure, pulse) | X | X | X | X | |
| Height | X | | | | |
| Weight | X | | | X | |
| Dietary counselling including alcohol consumption, and timing of statin vs. IP intake | X | X | X | | |
| Check compliance on statin and IP | | | X | X | |
| 12-Lead ECG | X | | | X | |
| Hematology | X | X | X | X | |
| AST, ALT, Creatinine | X | X | X | X | |
| Bilirubin | X | | | | |
| LDH, CPK | | X | X | X | |
| TG, TC, LDL-C, HDL-C | X | X | X | X | |
| LDL-C (direct-measured), VLDL-C, apo-B, Lp(a), non-HDL-C, small low-density lipoprotein (LDL) subclass particle concentration | | X | X | X | |
| HbA1c, Insulin, Glucose and hsCRP | | X | | X | |
| Concomitant medication | X | X | X | X | |
| Pregnancy test* | X* | X* | | | |
| Randomization | | X | | | |
| IP dispensing | | X | X | | |
| Adverse Events | X** | X** | X** | X** | X** |

*Female patients of childbearing potential will have a urine pregnancy test performed at the screening visit and at randomization (visit 2)

**Serious Adverse Events (SAEs) are captured from the time of consent through to week 14 safety Follow up phone call. AEs are captured between the time of randomization up to the last dose IP taken.

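### The AE capture window is stated inconsistently and the TEAE definition has no end date, so crude AE proportions could understate some event types if early stopping differs by arm

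*SAP*

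**What the plan says.** Collection of non-serious events is described in two ways.

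- Ending at last dose. Protocol 7.4: "All AEs will be captured between the time of randomization up to the last dose IP taken". Protocol 6.9: "Adverse events (serious and non-serious) will be collected throughout the study from randomization to last dose of IP taken". The footnotes to the visit schedules (protocol Appendix 2, SAP Appendix 1) attach the same limit to the AE row itself; in the SAP, "AEs are captured between the time of randomization up to the last dose IP taken".
- Continuing past last dose. Protocol 6.2: "Follow-up phone call will be performed 2 weeks after last dose taken for capturing any AEs". The protocol synopsis, protocol 3.1 and SAP 2.1 describe the Week 14 telephone contact as an assessment of AEs.

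Serious events have a longer window. SAP 5.2: "SAEs will be collected from the time of consent through to 2 weeks after the last dose of study product". Protocol 7.4 and the schedule footnotes run it to the Week 14 call instead, which is a different date for anyone who stops early.

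Stopping product does not end participation. Protocol 5.5: "The study participant should continue to be followed for all other study related procedures and visits". Protocol 4.3 says the same for subjects who consent to stay.

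On the analysis side, SAP 5.1 and 6.5.2.1 define a TEAE by a start point (first dose) and give no end. SAP 6.5.2.1 then reports the "number and proportion of subjects experiencing a treatment-emergent AE will be presented by system organ class and preferred term overall and for each treatment group". Exposure duration and treatment discontinuation are tabulated by group (SAP 6.5.1, Tables 3.1.1 and 3.1.2), but no AE table uses exposure as a denominator.

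**The concern.** If non-serious events are recorded only while a subject takes product, a subject who stops at Week 2 contributes 2 weeks of AE observation and a completer contributes 12, yet each counts as one in the denominator of the crude proportion. If one arm has more early stoppers, events that would have occurred later go unrecorded there more often, and its proportions for those events come out lower at equal underlying risk.

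Separately, with no end date on the TEAE definition, a single table can combine non-serious events seen up to last dose with serious events seen for two weeks more. If sites follow different passages, it can also combine non-serious events from different windows.

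Safety is a secondary objective, and protocol section 1 says the trial is needed to delineate the effective dosage. The by-arm AE tables are the only safety comparison it will produce, and the dose cohorts take 3, 6 or 12 tablets a day (SAP 6.3.6), so unequal stopping is plausible.

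**Working it through.** The documents state no AE rate and no early-stopping rate, so there is no planned figure to reproduce. All rates below are assumptions. From the documents: 12 weeks of treatment, 66 subjects per group, and placebo made up of three sets of 22.

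**1. Observation time under each reading**, for a subject who stops at Week 2 and stays in the study, against a completer:

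- to last dose: 2 vs 12 weeks;
- to two weeks after last dose: 4 vs 14 weeks;
- to a Week 14 call for everyone: 14 vs 14 weeks.

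Only the third reading removes the dependence on the subject's own last dose.

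**2. Stopping unrelated to AEs, equal true risk, capture to last dose.** With 12-week risk p, hazard r = −ln(1−p)/12. If a share s stops at week w, the crude proportion is (1−s)·p + s·(1−e^(−rw)). The gap between two arms is therefore (s₁−s₂)·[p − (1−e^(−rw))].

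Assumed grid: p = 30% or 50%; stopping 15% vs 5%, 25% vs 5% or 30% vs 10%; w = 2 or 4.

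- Smallest gap (p = 30%, 15% vs 5%, w = 4): 0.10 × (0.300 − 0.112) = 1.9 points.
- Largest gap (p = 50%, 25% vs 5%, w = 2): 0.20 × (0.500 − 0.109) = 7.8 points. The crude proportions are 40.2% and 48.0%, with potential on-treatment time averaging 0.75×12 + 0.25×2 = 9.5 weeks and 0.95×12 + 0.05×2 = 11.5 weeks.
- Equal stopping: 0.

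A wider grid (risk 10–50%, 9–30% stopping at day 14, 28 or 42), set against an arm in which nobody stops, gives shortfalls of 0.4 to 11.7 points. The top value is 0.30 × 0.391. It is an outer bound, because a comparator with no stopping at all is unlikely. At 9% stopping the range is 0.4 to 3.5 points, at most 2.3 of 66 subjects.

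**3. Capture to two weeks after last dose.** Same largest case: 0.20 × [(1−0.5^(14/12)) − (1−0.5^(4/12))] = 0.20 × (0.555 − 0.206) = 7.0 points. The gap shrinks a little and does not vanish.

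**4. Pooled placebo.** Each cohort has its own matching placebo, and the single placebo group pools them. If tablet burden drives stopping (25% at 12 tablets a day, 5% at lower counts), placebo stops at (5% + 5% + 25%)/3 = 11.7%. The 7.8-point gap becomes (0.250 − 0.117) × 0.391 = 5.2 points.

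**5. Stopping caused by an AE.** Let every subject with a gastrointestinal event (12-week risk g) stop at its onset, with an independent risk of 30% for other events and capture to last dose. Other events are then recorded with probability [λₒ/(λₒ+λ_g)]·[1 − (1−0.3)(1−g)], where λ = −ln(1−risk).

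- g = 30%: other events 0.5 × (1−0.49) = 25.5% instead of 30.0%; gastrointestinal events still 30%; any TEAE 1−0.49 = 51% under either window.
- g = 50%: other events [0.357/(0.357+0.693)] × 0.65 = 22.1% (22.0% in a simulation of 400,000 subjects); gastrointestinal events still 50%; any TEAE 65% under either window.

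The triggering event happens on treatment and is counted, and a subject whose observation is cut short has already entered the any-TEAE row.

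**6. Rates.** Under a constant hazard, subjects with an event divided by person-time to first event or last dose returns r in both arms: 2.97 per 100 person-weeks at p = 30%, whatever the stopping pattern.

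**The case against.** The last-dose cut-off is only one side of a conflict in the documents, and staff are to ask about AEs at all visits (protocol 7.4). That stands. It means the capture window has to be settled before the effect can be sized. It does not remove the issue, because a call two weeks after last dose still follows the subject's own stopping date.

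The gap needs unequal stopping, and the documents give no such figure. The only attrition figure is about 9% loss to follow-up, not split by arm. That also stands. Even 7.8 points is below one standard error of a between-arm difference at 66 per arm and 50% risk: √(2 × 0.25/66) = 8.7 points.

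The tables are descriptive with no safety testing (SAP 6.5). Exposure, discontinuation and TEAEs leading to withdrawal are shown by group, so a reader would see unequal observation time, and the withdrawal row would count against an arm that stops because of AEs. This is largely right, although per-term rates cannot be rebuilt from those tables.

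Rates have weaknesses too. They assume a roughly constant hazard; if events cluster early, they overstate risk in the early-stopping arm. They also inherit the SAP 6.5.1 rule that replaces a missing last-dose date with the earlier of the Week 12 visit or study completion, which can overstate exposure in early stoppers. Both points stand, and are reasons to keep the crude proportions.

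**Conclusion.** The point holds as a minor one. The capture passages conflict, the TEAE definition is open-ended, and the crude proportions take no account of observation time. If early stopping differs by arm and capture follows each subject's last dose, proportions for event types other than the one that caused stopping would be understated. Under the assumed rates the gap is roughly 0 to 8 points between arms, and about 5 rather than 8 against pooled placebo in the tablet-burden example.

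A reader might go further and infer that non-serious events are definitely collected only to last dose, so that an early-stopping arm looks safer by construction. The documents do not support that. Four places describe a later AE assessment, no stopping rates are given, the triggering event is fully counted, and the any-TEAE proportion is unchanged when AEs drive the stopping. Nor does the last-dose cut-off carry over to serious events, which are collected beyond it.

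**What to change.** - Reconcile the AE capture passages: protocol synopsis, 3.1, 6.2, 6.9, 7.4 and the Appendix 2 footnote, with SAP 2.1, 5.2 and the Appendix 1 footnote. One end point should be stated for non-serious events and one for serious events.
- Give the TEAE definition in SAP 5.1 and 6.5.2.1 an end date, so that serious and non-serious events are counted over the same on-treatment window. Show serious events after last dose separately in Tables 3.2.3 and 3.2.4.
- In Tables 3.2.1 and 3.2.2, add exposure-adjusted incidence beside the crude proportions: subjects with an event divided by person-time from first dose to first event or last dose, using the SAP 6.5.1 dates.

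The analysis changes cost some SAP wording, one added column, and programming of time to first event for each system organ class and preferred term, including a rule for incomplete onset dates. They need no new data. Because the rates rest on a roughly constant hazard and on the missing last-dose rule, the crude proportions should stay as the companion display.
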